- a) Gingival inflammation (MGI)

Secondary analyses were the comparison of data with respect to product effectiveness:

- a) Reduction in bleeding on probing (BOP) and Turesky modification of the Quigley-Hein Plaque Index (PI) grading on all natural teeth in the dentition

The primary statistical analytic framework was the repeated measures analysis of variance on three primary outcomes: probing depth, gingival index, and plaque. The primary hypothesis tested was the treatment by time interaction, i.e., did one treatment work better during the observations of these three outcomes? In other words, not just the total change, but also the rate of that change might differ between treatments. The proposed analysis was based on data that were generally normally distributed and similarly. If not, data transformations or link functions were used.

Outcomes

Raw data were collected from examinations of each tooth with regard to probing depth, gingival index, and plaque. Data were collected over three time periods, recorded into patient files, and transferred to Excel Workbooks, with one Workbook per patient. Each Workbook contained three tabs, one for each visit.

The raw data were combined as two levels of indexes for the three measures. The first outcome was a global score index of probing depth, gingival index, and plaque measurement. The global index was derived from individual tooth scores for each measure divided by the number of teeth measured. The second index derived from the same raw data described the three measures in terms of average scores for implant and non-implant teeth.

For the second analysis, implanted tooth data were separated from normal teeth data within each patient. Implant scores for each patient were averaged for probing depth, gingival index, and plaque scores. If a patient had one implant, each score was identical to the single measurement. With more than one implant, a single implant score for each patient was derived from averaging each of the three measures over the three observation periods. Likewise for each patient, the non-implanted teeth measures were averaged for each of the three times of assessment.

Individual patient data of the averages of the implant and non-implant teeth were calculated for each time period and transferred to a master data sheet.

Data Management and Statistical Analysis

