The patients' data on the three measures were recorded within the Excel Workbooks under three tabs representing the first, second, and third clinical observation periods. So each tab recorded three measures. The first and last tabs recorded probing depth, gingival index, and plaque. The second visit included only gingival index and plaque. Each patient had an individual Excel Workbook. Data were sorted into analysis format through two Excel macros that created a single master data for global scores and a single one for implant and non-implant scores. Data files were saved in comma separated value (csv) format in both wide and long formats for R and SPSS data management, inspection, cleaning, and analyses.

Since many individual variable distributions varied substantially from normal, a gamma log-link function was applied to reduce bias in most statistical tests.

Label Key and Lot #s for Peri-Implant Mucositis Study with Stony Brook University

Rowpar Pharmaceuticals, Inc., released the test material label codes after completion of the clinical study and statistical analysis of the data. The products were labelled as follows:

Study Number: SBU-RPR-Peri-Implant Mucositis-2018

Oral Rinse A: ClōSYS Placebo Oral Rinse, Lot #: 2-80516

Oral Rinse X: ClōSYS® Ultra Sensitive (Unflavored) Oral Rinse, Lot #: 8122A 14-80430

Results

Patients

Fifty-two percent (29/56) of patients in both groups had only one implant. Patients in the control group (Group A) had a total of 47 implants: 11 patients had just one implant, 13 had 2, 2 had 3, and 1 had 4 implants. In the test group (Group X), there were 42 total implants in 26 patients: 18 had 1 implant, 9 had 2, and 2 had 3 implants (see Figure 1). Table 1 gives average values (and standard error of the mean) of Gingivitis Index, Plaque score, and Probing depth at baseline.

Figure 1. Bar chart of numbers of implants per person in control group (Group A) and test group (Group X).

[figure not shown]

Table 1. Patient dental measures at baseline.

		n of patients	n of implants	Modified Gingivitis Index (MGI) (sem)	Plaque score (PS) (sem)	Probing Depth mean (sem)
Control Group (Group A)	implants	27	47	2.06 (0.048)	2.77 (0.115)	3.40 (0.109)

	non-implanted teeth			1.87 (0.039)	2.32 (0.101)	2.72 (0.099)
Test Group (Group X)	implants	26	39	2.82 (0.049)	2.84 (0.057)	2.447 (0.080)
	non-implanted teeth			2.01 (0.028)	2.99 (0.078)	2.65 (0.079)

Global Score Analyses

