Slope of probing depth, time 1 to 3	57	-1.47	0.015	-0.10632	0.323886
Slope of gingivitis index, time 1 to 3	57	-0.99	-0.03	-0.24351	0.221807
Slope of plaque score, time 1 to 3	57	-1.53	-0.045	-0.45254	0.358255
Valid N (listwise)	57				

Global Probing Depths (GPD)

Global probing depth (GPD) collected at the first visit did not differ significantly between groups; control group's (Group A) initial GPD was 2.76 (SEM = 0.092) interval, and 2.68 (0.071) for test group (Group X), a non-significant statistical difference ($p = 0.48$).

Neither did the GPD score differ between final visits of control group (Group A) (GPD = 2.64 (0.130) and test group (Group X) (GPDI = 2.37, (0.166), $t = 1.27$, $df = 55$, $p = 0.28$. Nonetheless, the GPD decreased significantly for control group (Group A), ($p = 0.028$; for X, $p < 0.001$) for both groups, but the group decreases were not significantly different from each other. Both mouthwashes reduced probing depth similarly.

The key signal of treatment effectiveness is a statistically significant treatment-by-time interaction, where improvement over time is greater for one treatment than another. Nearly parallel lines in Figure 2 and statistical testing indicated no appreciable and significant treatment-by-time interaction for GPD (See Figure 2, Figure 3).

Figure 2. Interaction plot showing that group assignment did not interact with time for probing depth.

[figure not shown]

Figure 3. Boxplots of probing depth results from treatment by control group (Group A) and test group (Group X). Probing depth was not affected differentially by the mouthwash treatments. Both conditions reduced probing depth slightly but not statistically significant.

Global Plaque Score

Control group (Group A) and test group (Group X) differed significantly in global plaque score (GPS) at initial assessment, requiring an additional analysis of covariance to confirm that a significant time by treatment interaction was not an artifact from the initial difference in GPS (See interaction plot, Figure 4, detailed in Figure 5). The test group's (Group X) initial average GPS was 3.00 (SEM = 0.071) versus 2.35 (0.097) for the control group (Group A), a significant difference ($t = -5.45$, $df = 50$, $p < 0.001$). At assessment 3, the last observation, the test group's (Group X) GPS (1.57, SEM = 0.110) was significantly lower than that for the control group (Group A); GPS = 1.98 (0.110), $t = 2.633$, $df = 55$, $p = 0.011$.

[figure not shown]

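### Section [11] makes MGI the only primary outcome, then names three, with no alpha or success rule; the named secondary BOP is never reported

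*Combined protocol and SAP*

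**What the plan says.** Section [11], Statistical Evaluation, gives one item under the primary objective: gingival inflammation measured by MGI. The secondary item is "Reduction in bleeding on probing (BOP) and Turesky modification of the Quigley-Hein Plaque Index (PI) grading on all natural teeth in the dentition". The following paragraph describes the framework as a "repeated measures analysis of variance on three primary outcomes: probing depth, gingival index, and plaque". Plaque is therefore both secondary and primary, and probing depth is primary without appearing in either list.

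The test itself is named: "The primary hypothesis tested was the treatment by time interaction". The results text repeats it under Global Probing Depths: "The key signal of treatment effectiveness is a statistically significant treatment-by-time interaction". Neither sentence gives a significance level or says how many outcomes must show the interaction.

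On BOP:
- The inclusion criteria in section [8] require it.
- Section [9] lists it at screening, at Visit 1 and at Visit 4.
- The Outcomes text describes the data without it: "Raw data were collected from examinations of each tooth with regard to probing depth, gingival index, and plaque".
- So does the workbook description: "The first and last tabs recorded probing depth, gingival index, and plaque".

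**The concern.** A reader cannot tell from the plan what result would have counted as success. Two incompatible statements of the primary outcome stand in the same section. Under the second, nothing says whether one, two or all three outcomes must be significant, or at what level.

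This matters because the three outcomes did not agree. Plaque and MGI favour the test rinse, while the report finds "no appreciable and significant treatment-by-time interaction for GPD". The same results can be called a success or a failure depending on a rule chosen afterwards. The Conclusions put plaque and gingival index side by side, although the first statement makes plaque secondary.

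Bleeding is a sign required for entry and one of two named secondaries, yet the report gives no treatment comparison for it.

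**Working it through.** **Inputs.** Table 2 (slopes of global scores, error df 55); Global Gingival Index Score (repeated-measures F = 8.141, p = 0.0046; ANCOVA t = 2.12, df 51, p = 0.039); Global Plaque Score (ANCOVA F = 34.82, p < 0.0001); Table 3. Alpha is not stated, so two-sided 0.05 is assumed; the report calls p = 0.039 significant, which fits.

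**1. Reported figures reproduced.** F = SS(group) / (SS(error)/55), with p from F(1, 55):
- MGI: 0.485 / (2.27/55) = 11.75 (stated 11.748), p = 0.0012.
- Plaque: 4.019 / (3.169/55) = 69.75 (stated 69.751), p = 2.3 × 10⁻¹¹.
- Probing depth: 0.125 / (5.75/55) = 1.196 (stated 1.191), p = 0.28.
- MGI ANCOVA: t = 2.12 on 51 df gives p = 0.0389 (stated 0.039).
- MGI repeated measures: the residual df is not given. On 1, 55 df, F = 8.141 gives p = 0.006, against the reported 0.0046.

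**2. Candidate rules.** Holm thresholds for three outcomes are 0.05/3 = 0.0167, 0.05/2 = 0.025 and 0.05.

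| Rule | Result on global scores |
|---|---|
| MGI sole primary, 0.05 | Positive on slope (0.0012), repeated measures (0.0046 or 0.006) and ANCOVA (0.039) |
| Three primaries, Holm, slopes | Plaque passes 0.0167; MGI passes 0.025; probing depth (0.28) fails |
| Three primaries, Holm, MGI by repeated measures | 0.0046 or 0.006 is below 0.0167, so MGI passes at any step |
| Three primaries, Holm, baseline-adjusted | Plaque passes; MGI at 0.039 misses 0.025 unless probing depth is at or below 0.025 |
| Fixed sequence, MGI first or plaque then MGI | MGI passes at 0.05 even at 0.039 |
| All three required | Fails on probing depth (0.28) |

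The adjusted Holm row is conditional because no probing-depth ANCOVA is reported.

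**3. Error rate if any one unadjusted win counted.** For independent tests, 1 − 0.95³ = 0.143. Simulating correlated normal outcomes gives about 0.125 at an assumed correlation of 0.5.

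**4. Conclusions against results.** The Conclusions give P < 0.001 for both gingivitis and plaque on difference scores and slopes. The global MGI slope is p = 0.0012. The Conclusions cite ANCOVA for plaque only; the adjusted MGI result of 0.039 is absent. Yet the gingival section says the covariate was included to avoid overstating the effect, the arms having differed at baseline (2.03 versus 1.91, p = 0.006).

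**5. BOP.** Section [9] has it at screening, Visit 1 and Visit 4. The section [4] schedule marks screening and Visit 4 but not Visit 1. No results text, table, figure caption or conclusion mentions it, so the missing figures do not explain its absence.

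**6. How far the p-values can be trusted.** Patient counts differ: 57 (Tables 2 and 3), 56 (Patients text), 54 (randomized) and 53 (Table 1). Table 3 shows minima of 0 at time 3 for MGI and for probing depth. Its MGI slope is (time 3 − time 1)/2: (1.48456 − 1.97158)/2 = −0.24351, as printed. The minimum slope of −0.99 needs a fall of 1.98, so zeros appear to enter the slopes. From N = 57, mean 1.48456 and SD 0.451688, removing 1, 2, 3 or 4 zeros leaves an SD of 0.409, 0.356, 0.290 or 0.193; removing five gives a negative variance. Removing one to four, with assumed slopes from −0.705 to −0.99 and every allocation of the zeros to arms, gives a largest MGI slope p of 0.013 (arms 27/30), 0.015 (28/29) and 0.017 (29/28). All are below 0.025. The ANCOVA cannot be re-derived from summary data.

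**The case against.** The strongest reply is that the conflict does not decide the main results. On the plan's own repeated-measures framework and on the Table 2 slopes, MGI survives a three-outcome correction. Plaque does too on its slope. ANCOVA was brought in as a check on baseline imbalance, not as the primary test. This stands, and it limits the point.

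Several stronger readings are tempting but not supported:
- **That multiplicity overturns the MGI finding.** It does not touch the unadjusted MGI or plaque results, and the 12.5–14.3% error rate applies only if any one win was enough.
- **That adjusted MGI definitely fails Holm.** This depends on a probing-depth ANCOVA that nobody has reported; the slope p of 0.28 is a different analysis.
- **That the P < 0.001 claim is wrong at every level.** Table 6 prints 0.000 for the group effect on gingivitis at site level, but that is a between-subjects test, not a test of slopes or difference scores. Table 5 prints 0.000 for time by group, but its title says probing depth and its measure label says GGI. The mismatch shown here is with the global MGI slope.
- **That probing depth fails everywhere.** The 0.28 is for the global index. The implant-section text calls a time-by-group interaction in probing depth significant but under 1%, and says depth did not change significantly in either group.
- **That screening and Visit 1 are rival baseline times for BOP.** Section [9] has both and allows them on the same day; only the schedule mark is missing.
- **That 51 ANCOVA df mean 54 patients.** What appears to be the same baseline plaque comparison (t of 5.45 in size) carries df 50 in one place and 55 in another, so df are not a safe guide to counts.
- **That BOP was withheld because it was unfavourable.** Nothing in the documents shows the reason.

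**Conclusion.** The point holds as a defect of specification and reporting. Section [11] contradicts itself on the primary outcome and supplies no rule to resolve the conflict.

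At the assumed two-sided 0.05, the choice of rule moves the trial from positive (MGI alone) to negative (all three required, global probing depth p = 0.28). It also determines whether the baseline-adjusted MGI result of 0.039 counts. It does not overturn the unadjusted MGI or plaque results. The Conclusions overstate global MGI on slopes (P < 0.001 against 0.0012) and leave out the adjusted figure. BOP, a named secondary and an entry criterion, is unreported.

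All p-values are taken as reported and stay provisional until the counts and zeros are explained. If the zeros are missing values, the MGI slope p still stays at or below about 0.017 in the splits tried.

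**What to change.** 1. Establish from a dated protocol version that predates the data which outcome was primary. If this cannot be shown, say so, use the first-listed MGI as single primary at two-sided 0.05, and label the choice post hoc. If three primaries are kept instead, state the alpha and the success rule.
2. Report the repeated-measures interaction and the baseline-adjusted MGI result together in the Conclusions, and correct the P < 0.001 statement for global MGI.
3. Present plaque, BOP and probing depth as ordered or Holm-adjusted secondaries.
4. Analyse BOP at teeth and implants from the examination records, or state that it cannot be retrieved. Align the schedule with the Visit 1 procedures.
5. Before restating any p-value, reconcile the counts (57, 56, 54, 53) and say whether the Table 3 zeros are scores or missing values. Do not derive a count from the ANCOVA df.

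The cost is revised wording and a re-run. Plaque loses primary status. BOP may be irretrievable, since the workbooks are described as holding only three measures. Because the results are known, all re-specification is post hoc.

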Samples for microbiome analysis were collected at baseline (Visit 1), Day 14 (Visit 2), and Day 90 (Visit 4). Before collecting samples, each patient was asked to rinse with plain water prior and rest for 5 minutes. Sample collection was performed by gently wiping the buccal and tongue mucosa separately 10 times with three different cotton swabs. Samples were allowed to air dry at room temperature and individually placed in labeled containers with the patient's unique sequential subject identification number and day of collection. These samples were stored in a secure location at -20°C until utilized for microbiome analyses.

[4] Study Design Table

Protocol Study Design and Schedule of Assessments

Evaluation	Screening (0-2wks to Baseline)	Baseline (Visit 1) Day 0	Visit 2 Day 14 (± 3 d)	Visit 3 Day 45 (± 7 d)	Visit 4 Day 90 (± 7 d)
Informed Consent	x				
Inclusion / Exclusion	x	x			
Demographics	x				
Pregnancy Test		x			x
Medical History / Update	x	x	x		x
Medications / Update	x	x	x		x
Periodontal History	x		x		x
Oral Examination	x	x	x		x
Collect Specimen w Swab		x	x		x
Modified Gingival Index / MGI		x	x		x
Bleeding On Probing / BOP	x				x
Probing depth	x	x			x
Turesky modification Plaque Index		x	x		x
Scaling	x				
Eligibility	x				
X-rays		x			x
Enrollment / Randomization		x			
Dispense oral hygiene kit / Diary		x			
Schedule next appt	x	x	x		
Collect residual oral hygiene kit with Diary and distribute oral hygiene kit with Diary for next phase			x	x	
Collect residual oral hygiene kit / Diary					x

[5] Protocol Synopsis

1. Study Title: The Efficacy and Safety of stabilized chlorine dioxide mouth rinse in Therapy of Peri-implant mucositis
2. Study Design: Single Center, randomized, double blind masking, parallel, two-arm clinical study.
3. Objective: The purpose of this study was to analyze efficacy of stabilized chlorine dioxide as a chemical adjuvant for treatment of peri-implant mucositis in a non-surgical treatment protocol with a 3-month follow-up.
4. Study Treatments: 1) Stabilized chlorine dioxide (associated with periodontal basic therapy); and 2) control (placebo associated with periodontal basic therapy).
5. Number of Patients: A total of 54 patients in one clinical site at Stony Brook were randomized, 27 patients received 1) Stabilized chlorine dioxide (associated with periodontal basic therapy); and 27 patients received 2) control (placebo associated with periodontal basic therapy).

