2. Checked record for use of test rinse or placebo in the diary.
3. Provided diary for recording use of product rinse or placebo.
4. Provided supplies for remaining 45 days (day 46 to day 90 of the study). Weighed and recorded the weight of test rinse or placebo, as applicable, being provided.
5. Confirmed appointment date scheduled for the Final Examination Visit (Visit 4). The subjects were given a reminder call 2 - 3 days prior to their scheduled appointment.

VISIT 4 - FINAL EXAMINATION – DAY 90

This examination took place within 90 days following the Baseline Examination (Visit 1) \pm 7 days. The following procedures were conducted:

1. Collected the subject's diary and unused products at check-in. All partially used products were assessed for volume remaining and recorded. Used products were retained until after a monitoring visit, and then returned to the Sponsor.
2. Performed pregnancy testing on females of childbearing age.
3. Rinsed mouth with water and collected samples for microbiome analysis by use of a cotton swab on the inside of the cheek and tongue mucosa.
4. Asked the subject to report any changes in medical or dental health since the last visit.
5. Evaluated extra- and intra- oral areas for any mucosal irritation or pathology.
6. Performed a Modified Gingival Index (MGI) grading on all natural teeth and implants in the dentition.
7. Performed a Turesky modification of the Quigley-Hein Index (PI) grading on all natural teeth and implants in the dentition.
8. Assessed bleeding on probing (BOP) and probing depth on all natural teeth and implants in the dentition.
9. X-rays
10. Weighed and recorded remaining test rinse or placebo as applicable.
11. Checked record for use of test rinse or placebo in the diary.

[10] Study Timeline

Using December 2018 as a calendar starting point, the entire month would provide 20 days for recruiting. As the screening, cleaning and baseline visit can be all on the same day we were considering that subjects could begin Study Visit 1 between January 2019 and December 2019. The final study visits was conducted in March 2020. A final report concluded by December 2020.

[11] Statistical Evaluation

The primary objective of this study was to analyze efficacy of stabilized chlorine dioxide as a chemical adjuvant for treatment of peri-implant mucositis in a non-surgical treatment protocol with a 3-month follow-up.

The primary objective was determined by an examination of the following data:

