From raw data of individual teeth, each patient received a global index of periodontal disease, gingival index, and plaque for each visit. The global index for each of these measurements was found by dividing the sums of patient probing depth, gingival index, and plaque findings collected for each tooth by the number of teeth assessed. Over the three assessment periods, global scores of probing depth, gingival index, and plaque were collected for the first and last visits with probing depth scores not collected during the second visit. These outcomes are measured as individual slopes of responses across the three observation visits. The slope represents the rate of change.

The overall view of the response of each measure to the treatment group is summarized in the following general linear model Table 2. Table 3 shows the cell statistics for the slopes of each condition and outcomes reported in Table 2.

Table 2. Master table of variance components attributable to treatment on individual rates of change on the three measures: probing depth, gingival index, and plaque.

Source	Variable	Type III SS	df	MS	F	Sig.
Group	Slope of probing depth, time 1 to 3	0.125	1	0.125	1.191	0.28
	Slope of gingivitis index, time 1 to 3	0.485	1	0.485	11.748	0.001
	Slope of plaque score, time 1 to 3	4.019	1	4.019	69.751	0.000
Error	Slope of probing depth, time 1 to 3	5.75	55	0.105		
	Slope of gingivitis index, time 1 to 3	2.27	55	0.041		
	Slope of plaque score, time 1 to 3	3.169	55	0.058		
Total	Slope of probing depth, time 1 to 3	6.519	57			

Slope of gingivitis index, time 1 to 3	6.135	57
Slope of plaque score, time 1 to 3	18.861	57
Corrected Total	Slope of probing depth, time 1 to 3	5.875
	Slope of gingivitis index, time 1 to 3	2.755
	Slope of plaque score, time 1 to 3	7.187
	R Squared = .021 (Adjusted R Squared = .003)	
	R Squared = .176 (Adjusted R Squared = .161)	
	R Squared = .559 (Adjusted R Squared = .551)	

Table 3. Details of cell statistics for analysis described in Table 2.

Descriptive Statistics					
	N	Minimum	Maximum	Mean	Std. Deviation
Probing depth at time 1	57	2.04	4.63	2.71614	0.432843
Probing depth at time 3	57	0	4.42	2.50351	0.804056
Gingivitis index at time 1	57	1.41	2.23	1.97158	0.172065
Gingivitis index at time 2	57	0	2	1.71754	0.364095
Gingivitis index at time 3	57	0	1.92	1.48456	0.451688
Plaque score at time 1	57	1.47	3.54	2.67895	0.555475
Plaque score at time 2	57	0	3.11	2.19614	0.596444
Plaque score at time 3	57	0	2.92	1.77386	0.618124

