The gingivitis index is based on the Gingival Index system,² in this case, the global gingival index is GGI. The GGI was also significantly higher for the test group (Group X) at the initial visit; for the test group (Group X) = 2.03 (0.025) and GGI for the control group (Group A) = 1.91 (0.035), ($t = -2.89$, $df = 55$, $p = 0.006$). Figure 6 illustrates a potential interaction between treatment and time of observation that required statistical consideration and control. Again, GGI for visit 1 was used as a covariate so as not to over-estimate treatment effects on GGI represented in a time-by-treatment interaction. The ANCOVA upheld a statistically significant ($t = 2.12$, $df = 51$, $p = 0.039$) between treatments. Boxplots of the GGI across visits is shown in Figure 7. The test group (Group X) reduction in GGI was 27.3% versus the control group's (Group A) reduction of 20.4%, also statistically significant difference by repeated measures analysis of variance ($F = 8.141$, $df = 1$, $p = 0.0046$).

[figure not shown]

Figure 6. Interaction plot showing group assignment interacting with time on gingival index measures (GGI).

[figure not shown]

Figure 7. Boxplots of gingival index measures comparing treatment control group (Group A) and test group (Group X). Test group (Group X) started with higher gingival index levels. Gingival index decreased more and faster in test group (Group X) than in the control group (Group A), though both decreased significantly.

Differential Effects of Mouthwashes on Implants in Control Group (Group A) and Test Group (Group X)

Of particular interest was the specific effect that control mouthwash (rinse A) and test mouthwash (rinse X) might have on implant and non-implant sites across the three outcomes. Table 4 illustrates the overall study results of treatments and implants on the three outcomes. Probing depth was not different between treatments for implant and non-implant sites. Plaque and gingival indexes were improved significantly under test rinse Treatment (rinse X), with details described in Tables 5, 6, and 7 below. In addition, implant sites improved at a faster rate under test rinse Treatment (rinse X) conditions for both gingivitis and plaque.

Table 4. Omnibus test for main effects and interactions of control mouthwash (rinse A) and test mouthwash (rinse X) on implant and non-implant sites.

Sites of Implants responding differently to treatment					
All outcomes: measures in table					

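### The primary treatment-by-time test keeps baseline in the response, and baseline adjustment is neither prespecified nor uniform: none is reported at implant sites, where the arms start far apart

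*Combined protocol and SAP*

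**What the plan says.** Section [11] Statistical Evaluation names MGI as the variable for the primary objective, then sets the framework: "The primary statistical analytic framework was the repeated measures analysis of variance on three primary outcomes: probing depth, gingival index, and plaque". It continues: "The primary hypothesis tested was the treatment by time interaction". No baseline covariate is mentioned. Under Global Score Analyses, "These outcomes are measured as individual slopes of responses across the three observation visits", so baseline is part of the response.

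Covariance adjustment first appears in the results:

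- **Whole-mouth plaque** (Global Plaque Score): the arms differed at baseline (p < 0.001), "requiring an additional analysis of covariance to confirm that a significant time by treatment interaction was not an artifact".
- **Whole-mouth MGI** (Global Gingival Index Score): the arms differed at baseline (p = 0.006), and "Figure 6 illustrates a potential interaction between treatment and time of observation that required statistical consideration and control". Visit 1 was then used as covariate.
- **Whole-mouth probing depth** (Global Probing Depths): baseline p = 0.48; no adjusted analysis is reported.
- **Implant sites** (Tables 4 to 7 and text): no baseline-adjusted analysis for any outcome, although Table 1 gives test against control MGI of 2.82 and 2.06, and probing depth of 2.45 and 3.40.

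The Conclusions describe difference scores and slopes as robust to the unequal starting levels of gingivitis and plaque, with P < 0.001 for both.

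**The concern.** When the arms start at different levels, the arm that starts higher can show the larger fall without any treatment effect. A change score, a slope or a time interaction that includes baseline does not remove this. It equals the adjusted effect only if the within-group coefficient of Day-90 score on baseline is 1. Adjusting some outcomes and not others, in a pattern that follows the baseline tests at whole-mouth level, also leaves open which p-value is the result. For whole-mouth MGI the documents hold three: 0.001 (slope, Table 2), 0.0046 (repeated measures) and 0.039 (ANCOVA). The Conclusions omit the last.

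Most is at stake at the implant sites. The disease under study is peri-implant, the imbalance is largest there, and the Conclusions claim a preferential benefit there.

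**Working it through.** **1. The documents' own whole-mouth MGI figures.** Table 2: F = 0.485 / (2.27/55) = 11.75 on 1 and 55 df, p = 0.0012 (stated 0.001). ANCOVA: t = 2.12 on 51 df, p = 0.0389 (stated 0.039). Both reproduce.

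**2. What the slope measures.** Table 3 mean MGI slope: (1.48456 - 1.97158)/2 = -0.24351, as printed. The slope is half the baseline-to-Day-90 change, so Table 2 is an unadjusted change-score test.

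**3. Bias of an unadjusted change.** With baseline gap g (test minus control) and within-group coefficient b, the adjusted difference is (Day-90 difference) - b × g, and the change difference is (Day-90 difference) - g. They differ by (1 - b) × g.

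**4. Whole-mouth MGI, back-calculated from Tables 2 and 3.** Assumed arm sizes are 29 and 28 (N = 57), with g = 2.03 - 1.91 = 0.12.
- 1/29 + 1/28 = 0.0702. Slope difference = √(0.485 × 0.0702) = 0.1845, so change difference = -0.369 and Day-90 difference = -0.369 + 0.12 = -0.249.
- Within-group sums of squares: baseline 56 × 0.172065² - 0.12²/0.0702 = 1.453; Day 90 56 × 0.451688² - 0.249²/0.0702 = 10.542; change 4 × 2.27 = 9.08.
- Cross-product = (1.453 + 10.542 - 9.08)/2 = 1.457, so b = 1.457/1.453 ≈ 1.00 (0.97 to 1.04 for g from 0.11 to 0.13).
- Adjusted difference ≈ -0.37, SE 0.116, t = -3.18, p = 0.0024.
- ANCOVA error mean square is 0.168 against 9.08/55 = 0.165 for change: no precision gain.

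These moments do not agree with the text. The stated reductions of 27.3% and 20.4% give changes of 2.03 × 0.273 = 0.554 and 1.91 × 0.204 = 0.390, a difference of 0.165 rather than 0.369.

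**5. Implant-site MGI.** From Table 1, g = 2.82 - 2.06 = 0.76, and 0.76/√(0.048² + 0.049²) = 11.1 standard errors. Implants and Gingival Index gives reductions of 26% and 19%, taken here as baseline to Day 90:
- Day 90: test 2.82 × 0.74 = 2.09; control 2.06 × 0.81 = 1.67; difference +0.42.
- Adjusted difference = 0.418 - 0.76b: +0.42 at b = 0, zero at b = 0.55, -0.34 at b = 1.

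The same section also gives 83% and 57%. Those imply Day-90 values of 0.48 and 0.89, and adjusted differences from -0.41 (b = 0) to -1.17 (b = 1), which favour the test rinse throughout. The two sets cannot both describe the same change.

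**6. Table 6 read as improvement.** The text cites F = 79.0 for more and faster improvement. In Table 6 this is implant × group among between-subjects effects, that is, averaged over visits including baseline. Assume 27 and 26 patients (the error df of 102 fits 53 × 2 - 4) and three visits. Then SS = 3C²/(2/27 + 2/26), so C = √(8.613 × 0.151/3) = 0.66. At baseline alone, Table 1 gives (2.82 - 2.01) - (2.06 - 1.87) = 0.62. Table 7 behaves the same way: for plaque, √(7.532 × 0.151/3) = 0.62 against a baseline contrast of (2.84 - 2.99) - (2.77 - 2.32) = -0.60. F gives size only, not sign, but both effects are about as large as the imbalance already present before treatment.

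**7. Error rates.** Simulation with 27 per arm, no effect and a two-sided 5% level (assumed; none is stated): change test about 5%, ANCOVA about 5%, ANCOVA only after a significant baseline test 4% to 5%. Given a baseline gap of z = 2.89, and assuming equal SDs and correlation 0.2 to 0.7, the change test falsely favours the test rinse 43% to 18% of the time. With an SD ratio of 2.6, as in Table 3 (0.4517/0.1721), the range is 7% to 0%.

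**The case against.** The strongest defence is that, under randomisation, an interaction including baseline is valid on average, and that for whole-mouth MGI adjustment barely moves the result (p = 0.0012 to 0.0024 on the N = 57 moments). That stands. It limits the harm to bias conditional on this imbalance and to choice of analysis. Step 4 does not extend to implant sites, whose coefficient is not reported.

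Several stronger readings are tempting but not supported:

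- **Adjusting only after a significant baseline test inflates type I error.** The simulation shows it does not. The trigger is itself inferred: the plan states no such rule, and implant-site probing depth differed at baseline (p < 0.001) without adjustment.
- **Adjustment would save a sizeable share of the sample.** That needs similar SDs at baseline and follow-up; Table 3 has 0.17 and 0.45, and step 4 shows no gain.
- **Adjustment takes MGI from p = 0.001 to 0.039.** The df fall from 55 to 51, so the patients or the model also differ.
- **The reported test ignores the 3-month endpoint.** Step 2 shows it compares half the change to Day 90.
- **The rising SD breaks sphericity.** This does not bear on one slope per patient. Table 3's minima of 0 at later visits may contribute to the rise; whether they are missing values is unknown.

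A fair last objection is that results are known, so any newly named lead analysis is informed by them. That too stands and is met by labelling.

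**Conclusion.** The point holds in this limited form. Baseline adjustment was not prespecified, was applied to two whole-mouth outcomes only, and is absent where the imbalance is greatest. Difference scores and slopes do not adjust for baseline, so the robustness claim in the Conclusions is unsupported.

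For whole-mouth MGI the conclusion survives; its strength is uncertain between the documents' own 0.039 and the back-calculated 0.002. For implant-site MGI the direction is open on the 26% and 19% figures (+0.42 to -0.34) and favours the test rinse on the 83% and 57% figures. A reader might infer that the implant-site benefit is absent or reversed. The documents do not show that, because they give neither the coefficient nor one consistent set of reductions.

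The figures rest on the arm sizes assumed in steps 4 and 6, on Tables 1 to 3 and 6 as printed, and on the percentages being baseline-to-Day-90 changes of the Table 1 means. An implant-site gap of 11 standard errors is far more than chance would ordinarily produce, so Table 1 should be checked against source data before any model is fitted.

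**What to change.** 1. For MGI, plaque and probing depth, at whole-mouth and implant level, report the Day-90 treatment difference with 95% CI adjusted for that outcome's baseline, whatever a baseline test shows. For MGI and plaque use a mixed model on the Day-14 and Day-90 visits with baseline, treatment, visit and treatment-by-visit, and unstructured covariance. For probing depth, which has one follow-up measurement, use ANCOVA.
2. State whether whole-mouth or implant-site MGI is primary, reconcile this with the list of three primary outcomes, and lead with the adjusted MGI result. Show the interaction and slope tests as supportive.
3. Stop citing between-subjects effects in Tables 6 and 7 as improvement, and withdraw the statement that difference scores and slopes are robust to the mismatch.
4. Reconcile 26%/19% with 83%/57%, and the analysis sets: "A total of 54 patients in one clinical site at Stony Brook were randomized", against N = 57 in Tables 2 and 3 and 51 df in the ANCOVA.
5. Label the re-analysis as specified after results were known.

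The cost is revised wording and a re-run on data already collected. The downside is that the MGI evidence may prove weaker than p = 0.001, and the implant-site claim may change.
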